### ***3. Secondary objectives:***

- Analyze the clinical characteristics and prevalence of sarcopenia in patients included in the study.
- Analyze the thickness and cross-sectional area of the muscles in all patients rectus femoris, vastus medialis, vastus lateralis, medial calf and the angle of pennation of the medial twin.
- Analyze the correlation between ultrasound parameters and analytical parameters (nutritional, inflammatory).
- Determine the relationship between muscle loss and treatment received

(dexamethasone, methylprednisolone, prednisone).

- Determine the relationship between muscle loss and days of hospitalization or severity of illness.

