Research efforts at this point in the pandemic should focus on in the longer-term consequences of the disease, sequelae such as sarcopenia in patients who have suffered COVID-19. At the same time, doctors must be every time more aware of the condition and its measurement integrated into clinical practice. The knowledge that studies such as the one proposed will provide will allow the development of specific interventions.

The risk of sarcopenia should be considered when conducting an evaluation of the risk / benefit of the established treatment (for example, dexamethasone), and assess a multidisciplinary treatment that includes dietary contributions.

*g. Objectives of the study.*

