**1. Main hypothesis:**

- Patients admitted for COVID-19 present a progressive loss of mass muscle, both due to the inflammatory state, decreased intake, bedridden due to hospitalization and derivative of treatment (eg corticosteroid therapy).

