**3. Secondary objectives:**

- Analyze the clinical characteristics and prevalence of sarcopenia in patients included in the study.
- Analyze the thickness and cross-sectional area of the muscles in all patients rectus femoris, vastus medialis, vastus lateralis, medial calf and the angle of pennation of the medial twin.

- Analyze the correlation between ultrasound parameters and analytical parameters (nutritional, inflammatory).
- Determine the relationship between muscle loss and treatment received (dexamethasone, methylprednisolone, prednisone).

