#### *c. Inclusion and exclusion criteria.*

Patients who meet the following criteria will be included:

- Over 18 years old, men or women.
- Main diagnosis is pneumonia due to COVID-19

- Subjects who, after having received the information on the design, the purposes of the project, the possible risks that may arise from it and that in any moment they can deny their collaboration, verbally grant their consent to participate in the study.

The exclusion criteria to participate in the study are:

- Refusal of the patient to participate in the study.
- Present a malignant neoplasm in active phase except Ca spino- or basal cell in local stage
- Clinical situation of agony.
- Amputation of limb (s).

*d. Origin of the data:*

The data will be collected prospectively.

*and. Schedule and expected date of completion:*

The study will begin in **February 2021**, with an estimated duration of **3 months** (1 month for application, 1 month for data collection, 1 month for results analysis and preparation of articles and / or communications).

*and. Sample size:*

Patients over 18 years of age who are admitted to the hospital and whose primary diagnosis and reason for staying is COVID-19 pneumonia. For a 95% confidence interval, with a precision level of 3%, an estimated loss in about 3% of muscle mass in COVID-19 patients for an admission less than 10 days, we hope to recruit 124 patients. A loss to follow-up rate has been estimated 0%.

Subjects will be followed up during hospitalization and one month after consultation. recruitment. The 30-day follow-up will be done by reviewing the history

clinic, and a telephone contact will be made.

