#### **Four. V ARIABLES IN EVALUATION**

Data to collect:

\* PRIMARY VARIABLE:

*to. Variables related to ultrasound:*

To collect these variables, the GE VENUE will be used, the linear probe will be used (5.5–7.5 MHz) (General Electrics Healthcare, Madrid, Spain).

All patients will undergo a muscle ultrasound upon admission to the center and prior to upon discharge, using the usual muscle sweep technique. The ultrasound will be performed on the rectus femoris, vastus medialis, vastus lateralis and medial calf muscles. They will be measured:

- Muscle thickness in its cross section (in mm), in the plane of maximum thickness

in longitudinal sweep

- Cross-sectional area (in  $\text{cm}^2$ ) in the plane of maximum area in the scan longitudinal
- Angle of penetration (in degrees) of the medial twin, using the base of the angle the deep muscle fascia and as an angle the maximum inclination of the you muscle mass.

This exam will be carried out by 5 experienced physicians according to the criteria of the ACEP (American College of Emergency Physicians) and who carry out more than 10 studies ultrasounds per week and at least 3 years of experience in the performance and interpretation of ultrasound examinations. A reliability study will not be conducted given the limitation in the time and current healthcare pressure.

In addition, to avoid the possible bias that inter-operator variability would suppose in these circumstances, the research team was provided with a training program and designed internal training consisting of:

- Theoretical course on basic, systematic musculoskeletal ultrasound, medication, etc.
- Practical seminars in which an ultrasound machine and healthy models will be used to your measurement.
- Supervised practical training with real hospital patients until assessing an adequate measurement of at least 5 patients.
- The team of 5 doctors adequately trained in this technique were specific to this trial to avoid protocol deviations and any other form of interoperator variability.

\* SECONDARY VARIABLES:

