**Table 1. Study development**

*and. Statistic analysis*

The variables will be expressed by total numbers and percentages for the variables categorical, and central values with measures of dispersion (mean and standard deviation / median and interquartile range if not normal distribution) for quantitative variables.

For the comparisons, the following statistical tests will be carried out: Chi and obtaining of the odds ratio with 95% confidence intervals (for the comparison of variables qualitative); Student's t (and Spearman test) (to obtain the difference of means / ranges); and Pearson's R (to determine the correlation between the variables quantitative). The data will be analyzed using SPSS statistical analysis software.

20.0.

Data in absentia will not be charged and will be left as lost.

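### The corticosteroid objective would be answered with unadjusted two-variable tests, although treatment is discretionary and the scan interval follows the length of stay

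*Combined protocol and SAP*

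**What the plan says.** The objective appears in the Summary (item 10) and again in section 2.g: "Determine the relationship between muscle loss and treatment received (dexamethasone, methylprednisolone, prednisone").

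The only analysis text is the Statistic analysis part of section 5. After descriptive statistics it states "For the comparisons, the following statistical tests will be carried out" and lists chi-square with odds ratios, Student's t with a Spearman test, and Pearson's R. It names no regression, covariate, stratification or per-day rate of loss.

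Four other places bear on this:

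- **Treatment.** Section 5.b, under usual intervention, leaves management to each responsible physician.
- **Scan timing.** Section 4 says "All patients will undergo a muscle ultrasound upon admission to the center and prior to upon discharge". No day is fixed for the second scan.
- **Causes of loss.** The main hypothesis in section 2.g calls the loss progressive and explains it as "both due to the inflammatory state, decreased intake, bedridden due to hospitalization and derivative of treatment (eg corticosteroid therapy").
- **Stay and severity.** The Summary has a separate objective, "Determine the relationship between muscle loss and days of hospitalization or severity of illness". It is a question of its own, not an adjustment, and the section 2.g list does not contain it.

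**The concern.** Treatment is not randomised, so treated and untreated patients may differ in ways that also affect muscle. The interval over which loss accrues is roughly the stay itself. A group that stays longer has more time to lose muscle, whatever drug it receives. By the protocol's own hypothesis there are competing causes, and the listed tests cannot separate them from treatment.

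Exposure measured in days has the same problem. Annex I records corticosteroid days. In-hospital steroid days cannot exceed the stay, and the stay also sets the scan interval. A Pearson correlation of steroid days with loss would therefore tend to be positive even without a steroid effect.

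A crude association would be real as an association. It misleads only if read as a steroid effect, and the protocol invites that reading. The main hypothesis lists corticosteroid therapy as a cause, and section 2.f says the risk of sarcopenia "should be considered when conducting an evaluation of the risk / benefit of the established treatment (for example, dexamethasone").

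**Working it through.** **The plan's own figures.** The 124 in section 3 is the precision formula for a proportion: 1.96² × 0.03 × 0.97 / 0.03² = 124.2. The Summary's 64 reproduces as the per-group size of a one-sided test of 20% against 40% (alpha 0.05, power 0.80). Neither was derived for the steroid comparison. Both are used below only as possible totals.

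**Inputs.** Only n comes from the documents. The rate of 0.3 points of percentage loss per day is a linear reading of the sample-size text, "estimated loss in about 3% of muscle mass in COVID-19 patients for an admission less than 10 days" (3/10). The following are assumed:

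- SD of loss 5 or 10 points
- within-group SD of stay 3 days
- 50% or 80% treated
- the difference in mean stay between treated and untreated (the gap)
- no true steroid effect

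**Step 1: only stay differs.** The false difference is d = rate × gap. The total SD is √(SD² + (rate × 3)²), SE = total SD × √(1/n₁ + 1/n₀), and the noncentrality is d/SE. Rejection is two-sided at 5% from the noncentral t with n − 2 degrees of freedom.

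Example with n=124, half treated, SD 5, gap 5: d = 0.3 × 5 = 1.5; total SD = √(25 + 0.81) = 5.08; SE = 5.08 × √(1/62 + 1/62) = 0.912; noncentrality 1.64; rejection 37.1%.

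| n | Points/day | Gap (days) | 50%, SD 5 | 50%, SD 10 | 80%, SD 5 | 80%, SD 10 |
|---|---|---|---|---|---|---|
| 124 | 0.3 | 1 | 6.2% | 5.3% | 5.8% | 5.2% |
| 124 | 0.3 | 3 | 16.5% | 7.9% | 12.3% | 6.8% |
| 124 | 0.3 | 5 | 37.1% | 13.1% | 25.8% | 10.2% |
| 124 | 0.3 | 7 | 62.7% | 21.1% | 44.9% | 15.3% |
| 124 | 0.15 | 5 | 13.1% | 7.0% | 10.2% | 6.3% |
| 124 | 0.6 | 5 | 87.7% | 37.1% | 70.6% | 25.8% |
| 64 | 0.3 | 1 | 5.6% | 5.2% | 5.4% | 5.1% |
| 64 | 0.3 | 5 | 21.4% | 9.1% | 15.5% | 7.6% |
| 64 | 0.3 | 7 | 37.0% | 13.1% | 25.8% | 10.2% |

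**Step 2: severity differs too.** Treated patients are assumed 1 SD sicker, at 1.5 points of loss per SD. The expected false extra loss is 5 × 0.3 + 1 × 1.5 = 3.0 points. Severity is either measured perfectly or through two proxies with joint reliability 0.5. Simulation, 4000 runs, n=124, half treated, SD 5, gap 5:

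| Analysis | Rejection | False extra loss (points) | 95% CI half-width |
|---|---|---|---|
| Unadjusted | 88% | 3.02 | 1.88 |
| Stay only | 23% | 1.52 | 2.44 |
| Severity and stay, perfect | 5.5% | 0.02 | 2.54 |
| Severity and stay, proxies | 9.8% | 0.76 | 2.52 |
| Severity without stay, perfect | 31% | 1.51 | 2.05 |
| Severity without stay, proxies | 60% | 2.26 | 2.00 |

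Variations, as unadjusted against severity and stay (perfect to proxies):

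- SD 10: 38% against 5-6%
- 80% treated: 72% against 5-9%
- gap of 3 days: 71% against 5-10%
- n=64: 60% against 6-7%
- no gap and no severity difference: every analysis 4-5%

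**Step 3: a separately built simulation.** Stay and severity correlate 0.5, each moves loss by 0.2-0.5 residual SD per SD, and the odds of steroid use rise 1.5- to 3-fold per SD of severity. The unadjusted test rejects in 9-81% (n=124) or 7-53% (n=64), and the adjusted model in 4-6%. If severity does not drive prescribing, both stay near 5%.

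**The case against.** The strongest reply is that the objective is secondary and speaks only of a relationship. Section 5 is silent on adjustment and does not exclude it. On this view, labelling the result unadjusted and descriptive would be enough, above all at n=64. The wording is as described. However, section 5 lists the tests that will be done, and adjustment chosen after seeing the data is weaker than adjustment fixed in advance. A label alone would leave the stated objective less well answered, using data that are largely collected anyway.

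The second reply concerns size, and it stands. Gaps of 5-7 days are large beside a planning figure of under 10 days. With a 1-day gap and treated patients 0.3 SD sicker, the crude test rejects in only about 12% (SD 5) or 6-7% (SD 10) at n=124. Five operators scan and section 4 rules out a reliability study, so the SD could exceed 10. At SD 15 the 88% case falls to about 18-20%. The figures show a mechanism and are not a forecast.

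The third reply is that the fix is imperfect, and this is partly right:

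- Admission SpO2 is hard to interpret without oxygen support. Annex I has oxygen and ventilation fields, but no admission timing is visible for them.
- A yes/no exposure leaves the named drugs to description, and the documents do not show that an untreated group of useful size will exist.
- Patients who die have no discharge scan. That is a separate selection problem which the regression does not remove.
- With imperfect proxies, 0.76 points of false loss remain.

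**Conclusion.** The point holds. Followed as written, the plan answers the corticosteroid objective with tests that cannot separate treatment from length of stay or from the other causes of loss that the protocol names. That much rests on the documents alone. The amount of bias does not: it depends on whether steroid use goes with severity or stay, which the documents do not say. Under the assumptions shown, crude rejection runs from about 5%, where groups hardly differ, to about 88%, where they differ strongly in both. The main objective, quantifying the loss, is not affected. This should be changed, but it does not threaten the study's central result.

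**What to change.** Add to the Statistic analysis part of section 5, for this objective:

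1. **Model.** A linear regression with the discharge value of one named muscle measure as outcome. Section 4 gives nine per side (4 muscles × 2 measures + 1 angle); treat the others as exploratory.
2. **Exposure.** One definition from Annex I, for example any systemic corticosteroid during the stay, yes/no. Describe drug, days and maximum dose separately.
3. **Adjustment.** Admission value of the same measure, age, sex, admission SpO2, admission CRP, and days between scans.
4. **Sensitivity analysis.** The same model without days between scans, because treatment may itself affect stay. State that this version leaves in any difference due to stay.
5. **Dates.** Make sure both scan dates are recorded. None is visible in Annex I as extracted, where the tables are broken.
6. **Reporting.** Label the two-variable tests descriptive. Report the adjusted result as an association with possible residual confounding by severity, intake and immobility.

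Apart from confirming the dates, the variables are already collected. The model has 7 terms: 124/7 ≈ 18 patients per term, but only 64/7 ≈ 9 at the Summary's size. Precision falls. In the scenario of step 2 the 95% CI half-width rises from 1.9 to 2.5 points (n=124) or from 2.7 to 3.7 (n=64), about 35-40% wider. Those half-widths are in points of percentage loss, while the outcome here is in mm, cm² or degrees, so only the relative widening carries over. Adjusting the exploratory measures as well would need more models.

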### **3. T Y P E O F E S T U D I O A N D D E S I G N**

#### *to. Clinical study phase*

Observational validation study of prognostic test based on clinical parameters, analytical and ultrasound.

#### *b. Definition of study population*

Patients over 18 years of age who are admitted to the hospital and whose primary diagnosis and reason for staying is COVID-19 pneumonia. For a 95% confidence interval, with a precision level of 3%, an estimated loss in

about 3% of muscle mass in COVID-19 patients for an admission less than 10 days, we hope to recruit 124 patients. A loss to follow-up rate has been estimated 0%.

Subjects will be followed up during hospitalization and one month after the time of recruitment. The 30-day follow-up will be done by reviewing the history clinic, and a telephone contact would be made.

After signing the Informed Consent, the parameters included in the Data Collection Notebook, included in Annex I.

All examinations will be labeled by a unique code, the history number clinic and archived in digital format.

#### *c. Inclusion and exclusion criteria.*

Patients who meet the following criteria will be included:

- Over 18 years old, men or women.
- Main diagnosis is pneumonia due to COVID-19

- Subjects who, after having received the information on the design, the purposes of the project, the possible risks that may arise from it and that in any moment they can deny their collaboration, verbally grant their consent to participate in the study.

The exclusion criteria to participate in the study are:

- Refusal of the patient to participate in the study.
- Present a malignant neoplasm in active phase except Ca spino- or basal cell in local stage
- Clinical situation of agony.
- Amputation of limb (s).

*d. Origin of the data:*

The data will be collected prospectively.

*and. Schedule and expected date of completion:*

The study will begin in **February 2021**, with an estimated duration of **3 months** (1 month for application, 1 month for data collection, 1 month for results analysis and preparation of articles and / or communications).

*and. Sample size:*

Patients over 18 years of age who are admitted to the hospital and whose primary diagnosis and reason for staying is COVID-19 pneumonia. For a 95% confidence interval, with a precision level of 3%, an estimated loss in about 3% of muscle mass in COVID-19 patients for an admission less than 10 days, we hope to recruit 124 patients. A loss to follow-up rate has been estimated 0%.

Subjects will be followed up during hospitalization and one month after consultation. recruitment. The 30-day follow-up will be done by reviewing the history

clinic, and a telephone contact will be made.

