### ***11. Study population and total number of patients***

Patients over 18 years of age who are admitted to the hospital and whose primary diagnosis and reason for staying is COVID-19 pneumonia. The prevalence of sarcopenia in hospitalized patients is 15-20%. Assuming a alpha risk of 0.05 and beta risk of 0.2 in a one-sided contrast, 64 subjects are required to detect a difference equal to or greater than 20% loss of muscle mass. It has been an estimated loss to follow-up rate of 0%.

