**2. Main objective:**

- Quantify the loss of muscle mass in hospitalized patients in areas of Medicine Inmate diagnosed with COVID-19.

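### The 3% precision claimed for 124 patients matches a single-proportion formula and is not established for a continuous paired outcome; the summary gives a different sample size, 64

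*Combined protocol and SAP*

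**What the plan says.** The main objective (Section 1, item 10, and Section 2.g) is descriptive: "Quantify the loss of muscle mass in hospitalized patients".

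Section 3 gives the sample size twice in the same terms, under the study population definition and under the sample size item. The basis is "For a 95% confidence interval, with a precision level of 3%, an estimated loss in about 3% of muscle mass", and the result is attached to "about 3% of muscle mass in COVID-19 patients for an admission less than 10 days, we hope to recruit 124 patients". Loss to follow-up is put at 0%. No formula and no SD are given, and the text does not say whether 3% precision is absolute or relative.

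Item 11 of the summary (Section 1) gives another size on another basis. With one-sided alpha 0.05 and beta 0.2, it says "64 subjects are required to detect a difference equal to or greater than 20% loss of muscle mass". The sentence before it cites a sarcopenia prevalence of 15–20% in hospitalized patients. No SD is given there either.

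The primary variable (Section 4) is ultrasound, with the timing "All patients will undergo a muscle ultrasound upon admission to the center and prior to upon discharge". The measures are continuous: thickness ("Muscle thickness in its cross section (in mm), in the plane of maximum thickness"), cross-sectional area in cm² and an angle in degrees. The statistical analysis in Section 5 summarises quantitative variables by "central values with measures of dispersion (mean and standard deviation / median and interquartile range if not normal distribution".

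**The concern.** For a mean change within patients, the width of the confidence interval depends on the number of pairs and the SD of the change. The expected size of the change does not enter. The sample size statement does the reverse: it gives an expected value (3%) and no SD. That is the input list for estimating a proportion, where the variance p(1 − p) follows from the expected value. But 3% here is an amount of muscle lost, not a share of patients, and no section defines a yes/no loss event with an expected frequency of 3%.

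Precision is the only reason offered for 124, and quantifying loss is the main objective. If the basis does not fit the outcome, a reader cannot tell whether the study will estimate the loss more or less precisely than stated. A reader of the summary alone would also come away with about half the sample size, aimed at an effect nearly seven times as large (20% against 3%).

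**Working it through.** **Inputs from the protocol.** Section 3: 95% confidence, precision 3%, expected loss 3%, N = 124, 0% lost. Summary item 11: one-sided alpha 0.05, beta 0.2, 20% loss, N = 64. **Not in the protocol:** the SD of change, so every SD below is an assumption. Precision is read as 3 absolute percentage points.

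**1. Reproducing 124.** Single proportion, n = z² p(1 − p) / d², with z = 1.96 and p = d = 0.03:

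1.96² × 0.03 × 0.97 / 0.03² = 124.2

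This is 124 to the nearest integer. A one-sided z gives 87.5 and does not match. The formula is therefore inferred from the match; the protocol does not name it.

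**2. Could a mean-based formula give 124?** n = (1.96 × SD / 3)². With SD = 17 this is (1.96 × 17 / 3)² = 123.4, or 124 rounded up. It works, but only with an SD of about 17 points that the protocol does not state.

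**3. What 124 and 64 pairs deliver for a mean percent change.** Half-width = t(n − 1) × SD / √n, with t(123) = 1.9794 and t(63) = 1.9983. The last two columns give the pairs needed for ±3 points.

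| Assumed SD (points) | Half-width, 124 pairs | Half-width, 64 pairs | Pairs for ±3 (1.96 formula) | Pairs for ±3 (t interval) |
|---|---|---|---|---|
| 5 | 0.9 | 1.2 | 11 | 14 |
| 10 | 1.8 | 2.5 | 43 | 46 |
| 15 | 2.7 | 3.7 | 97 | 99 |
| 20 | 3.6 | 5.0 | 171 | 174 |
| 25 | 4.4 | 6.2 | 267 | 270 |

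The SD at which the half-width is exactly 3 points is 3 × √124 / 1.9794 = 16.9 for 124 pairs, and 3 × √64 / 1.9983 = 12.0 for 64 pairs.

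**4. The relative reading.** If 3% precision meant 3% of the 3% loss, the half-width would be 0.03 × 3 = 0.09 points. Then 124 would need an SD of 0.09 × √124 / 1.96 = 0.5 points. The match in step 1 favours the absolute reading.

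**5. Where 64 may come from.** A one-sided comparison of two proportions, 20% against 40%, at 80% power gives, with pooled variance under the null:

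(1.645 × √(2 × 0.3 × 0.7) + 0.842 × √(0.2 × 0.8 + 0.4 × 0.6))² / 0.2² = 63.9, or 64 **per group**

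This study has a single cohort. Read instead as a one-sided paired test of a 20-point loss, 64 would imply an SD of change of 20 × √64 / (1.645 + 0.842) = 64 points. Both readings are inferences. Neither links 64 to 124.

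**The case against.** The strongest reply is that no harm has been shown. With 124 pairs the 3-point target is met at SDs of 5, 10 and 15 and missed at 20 and 25, and the protocol supports none of these over another. In a descriptive study the reported interval will use the observed SD, so a poor planning formula biases neither the estimate nor its interval. This stands, and it is why the point is not that 124 is too few.

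Second, the proportion formula is inferred, and the usual rounding up of 124.2 would give 125. A mean-based calculation with an SD near 17 cannot be excluded. That is also fair, but the conclusion does not depend on which formula was used: on either route the SD that fixes the precision is missing.

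Third, the plan does have categorical summaries and a prevalence objective, so proportions are not foreign to it. The sample size statement nevertheless ties its 3% to an amount of muscle, so this does not rescue the calculation.

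Fourth, 64 was derived as a test, so judging it by interval width says little about its own purpose. The 64-pair column shows only what follows for precision if 64 were the number recruited. The conflict between 64 and 124 is visible in the text and needs no assumed SD.

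**Conclusion.** The point holds in two parts.

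- **Precision.** The 3% precision claimed for 124 patients is not established for the primary outcome. It is true only if the SD of percent change is below about 16.9 points, and no SD of change is stated. This rests on an absolute reading of 3%, a mean percent change as the estimand and 124 complete admission–discharge pairs. Any missing discharge scan lowers the SD limit. The nominal target of 3% ± 3% runs from 0 to 6, so even if met exactly it would barely separate the expected loss from none. That describes the target and does not predict the result.
- **Two sample sizes.** 64 and 124 differ in number, effect size (20% against 3%) and framework (one-sided test against interval precision), and they are not reconciled. This part rests on no assumption.

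The plan should be corrected here, but nothing shows that recruiting 124 would fail the main objective.

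**What to change.** In both places in Section 3, replace the calculation with the precision of a paired mean. Name one ultrasound measure, for example percent change in rectus femoris cross-sectional area (the choice is the team's), and state the assumed SD of change and its source. Recruitment can stay at 124. Suggested wording:

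*With 124 patients measured at admission and before discharge, and an assumed SD of percent change in [measure] of [X] points ([source]), the 95% confidence interval for the mean change has a half-width of 1.9794 × X / √124 = 0.178 × X percentage points.*

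Add the half-widths for SDs of 5 to 25 points. Keep the 3-point claim only if the assumed SD is below about 16.9; otherwise restate or drop it. Say that the precision is in absolute percentage points.

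In summary item 11, replace the 64-subject calculation with the same figure and basis, or explain what the 64 refers to.

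The cost is rewording in three places. The stated precision may become less favourable. If the team keeps a 3-point target with an assumed SD above about 16.9, then 124 pairs are not enough (174 at an SD of 20, 270 at 25, by the t interval), and the target must be relaxed or more patients recruited.

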## 5. METHODOLOGY

*to. Selection of study cases*

Patients over 18 years of age who are admitted to the Hospital and whose primary diagnosis is COVID-19 pneumonia.

For this, patients who meet the criteria of inclusion. After granting verbal consent, the parameters included in the Data Collection Notebook, included in Annex I.

All examinations will be tagged with a unique code and history number Hospital clinic, and archived in digital format.

*b. Information collection:*

Once the patient has been recruited, the objectives and procedures of the study will be explained, He will provide the information sheet and you will be asked for your informed consent.

Then, according to the usual clinical practice, an evaluation will be carried out clinic that includes anamnesis, physical examination and extraction of laboratory tests, as well as other complementary tests that are considered appropriate for the patient's situation. A) Yes Also, at the time of the first assessment, a muscle ultrasound of the lower limbs, repeating it prior to discharge. All the variables collected will be collected in section 4 of this protocol.

The duration of the follow-up will be 30 days, the presence of complications in this time, by reviewing the medical history, as well as functional recovery (Barthel scale), and will be contacted by telephone, to pass a quality questionnaire of life (EuroQol-5D).

Any unexpected event that requires treatment or medical care, including mortality. Any undesirable effects will be collected observed, during hospitalization, and during follow-up for the next 30 days.

*\* The patient's CRF will include:*

Demographic variables, physical examination, laboratory findings, related to the diagnosis, treatment, as well as clinical evolution (see Annex I).

*\* Usual intervention:*

According to the usual management of COVID-19 infection, individualizing its use at the discretion of the responsible physician.

It must be taken into account that **the use of ultrasound will be carried out according to the current international recommendations (detailed below), and that strict measures will be followed to avoid contagion, it does not imply under any circumstances delay in the administration of treatment.**

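### The 124 allows for no missing pre-discharge scan, and the plan does not say that the muscle-loss estimate would describe only patients discharged with two scans

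*Combined protocol and SAP*

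**What the plan says.** The sample size paragraph appears twice in Section 3, under the definition of the study population and under Sample size. It gives 95% confidence, 3% precision, an expected muscle loss of about 3% for stays under 10 days, and 124 patients. It then states: "A loss to follow-up rate has been estimated 0" per cent. Summary item 11 makes the same assumption for a different calculation, which is not assessed here: "It has been an estimated loss to follow-up rate of 0" per cent. Neither place gives a reason.

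The primary variable in Section 4 needs two examinations: "All patients will undergo a muscle ultrasound upon admission to the center and prior to upon discharge". Section 5.b repeats this, describing "a muscle ultrasound of the lower limbs, repeating it prior to discharge". The Statistic analysis paragraph says of missing values: "Data in absentia will not be charged and will be left as lost". I read this as no imputation.

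The plan also provides for incomplete follow-up. Section 5.c ends follow-up at death if that comes before day 30, the inclusion criteria let patients withdraw at any time, and the data collection notebook (Annex I) has a field for loss to follow-up and mortality. The main objective, in the Summary and in Section 2.g, is to quantify muscle loss in hospitalized patients with COVID-19. It does not mention having two scans or being discharged alive.

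**The concern.** The stated precision holds only if every recruited patient supplies the primary measurement. A patient who dies in hospital has no pre-discharge scan, and one who withdraws or is not re-examined has none either. With no imputation, such patients contribute no change value.

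Two things follow. The number of pairs may fall below 124, so the interval would be wider than stated. And the patients who drop out of the estimate are unlikely to be a random subset, because death in hospital is one way of being left out. The plan links muscle loss to inflammation, reduced intake, bed rest and treatment, and the Summary lists a secondary objective on severity, so patients without a second scan may differ on what is being measured. A result from patients scanned twice could then be read as the loss in all hospitalized COVID-19 patients, and the plan does not commit to reporting what a reader would need to judge the difference.

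**Working it through.** **Inputs.** From Section 3: z = 1.96 (95%, two-sided), p = 0.03, d = 0.03, N = 124, loss 0%. The share without a second scan, m, is not in the documents; 5%, 10%, 15% and 20% are assumptions.

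**Step 1: reproduce the 124.** n = z² × p × (1 − p) / d² = 3.8416 × 0.0291 / 0.0009 = 124.2. The plan's figure is reproduced by rounding to the nearest whole number (rounding up would give 125, which is immaterial). The formula has no term for loss, so 124 is a zero-loss figure.

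**Step 2: effect of missing second scans at 124 recruited.**
- Pairs = 124 × (1 − m).
- Relative widening = 1/√(1 − m) − 1. This does not depend on the SD, provided the SD is the same in the patients who remain.
- Half-width on the plan's own formula = 1.96 × √(0.03 × 0.97 / pairs), in percentage points.
- Largest SD of percent change for which a mean would still have a 3-point half-width = 3 × √pairs / 1.96.

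| Assumed m | Pairs | Widening | Half-width, plan's formula | Largest SD for a 3-point half-width of a mean |
|---|---|---|---|---|
| 0% | 124 | – | 3.00 | 17.04 |
| 5% | 117.8 | 2.6% | 3.08 | 16.61 |
| 10% | 111.6 | 5.4% | 3.16 | 16.17 |
| 15% | 105.4 | 8.5% | 3.26 | 15.71 |
| 20% | 99.2 | 11.8% | 3.36 | 15.24 |

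The fourth column follows the plan's formula only; it is not the precision of a mean loss. The plan states no SD for the percent change. Using a proportion formula for a mean is a separate issue.

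**Step 3: who is in the estimate.** Sections 4 and 5.b define the measurement at admission and before discharge. The Statistic analysis paragraph leaves missing values missing. Together these give a within-patient change only for patients who reach discharge with both scans. No sentence says so, no analysis set is defined, and the objective is worded more widely.

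**Step 4: what could be reported.** Annex I already holds age, admission muscle measurements, oxygen saturation, CRP, and the loss and mortality field. It has no field for why a second scan was not done.

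**The case against.** - **The 0% may refer to the 30-day contact.** It is followed directly by the description of follow-up by record review and telephone. That reading is fair, but then no allowance at all is made for a missing second scan, and the gap remains.
- **The plan limits the problem.** It excludes "Clinical situation of agony", expects stays under 10 days, and says of the examiners: "The team of 5 doctors adequately trained in this technique were specific to this trial". These steps should reduce missing second scans. They do not cover later deterioration, death or withdrawal.
- **The precision effect is small.** This stands. Over the 0% to 20% range, the loss assumption decides whether a mean meets the 3-point target only if the SD lies between about 15.2 and 17.0 points. Below that the target is met anyway; above it the target is missed even with no loss.
- **The two-scan population is an inference.** This also stands in part. The analysis paragraph lists Student's t without saying paired, and an unpaired comparison of admission and discharge means would use every admission scan. The two-scan population is the natural reading, but the plan should state it.
- **Deaths and losses would be counted anyway.** The notebook records them and descriptive counts are planned. What is missing is the count without a second scan and a comparison of those patients with the rest.

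A reader might take the ECMO field in Annex I, or the sentence "A reliability study will not be conducted given the limitation in the time and current healthcare pressure", as evidence that many second scans will be missed. Neither supports that: the first is one box in a treatment list, and the second explains only why reliability is not studied.

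**Conclusion.** The point holds, with limited force on precision. The 124 is a zero-loss figure for an outcome that needs a second scan, in a plan that itself provides for death and loss. At an assumed 5% to 20% missing, about 118 to 99 pairs remain, the interval is 2.6% to 11.8% wider, and the half-width on the plan's own formula goes from 3.0 to between 3.1 and 3.4 points. Every missing rate here is an assumption.

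The more important part is interpretation: the estimate would describe patients discharged alive with two scans, under an objective worded for hospitalized COVID-19 patients in general. This rests on reading the change as within-patient, which the plan implies but does not state.

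A reader might infer that the study will miss its precision target because of the 0%, or that it will understate muscle loss. The documents support neither. They give no SD and no missing rate, and nothing in them fixes the direction or size of a bias.

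**What to change.** 1. In Section 3, replace 0% with an assumed non-zero share of patients without a second scan, labelled as an assumption and shown over a range such as 5% to 20%. Restate the precision for the expected pairs at 124 recruited. No extra recruitment is needed.
2. In the objective and the Statistic analysis paragraph, state that the primary estimate is the within-patient change in patients discharged alive with both scans, and limit the conclusion to them.
3. Report the number without a second scan, with deaths separate. Compare these patients' admission data already in Annex I (age, muscle measurements, oxygen saturation, CRP) with those of patients with two scans. Reasons other than death or recorded loss need one added line in the notebook.

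The cost is a few sentences, a slightly less favourable stated precision, one extra table and, if reasons are wanted, one notebook line. No imputation is needed.
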